**C.4.6 Response Inhibition Task for fMRI:** An event-related Go/NoGo task [1] is used for fMRI of response inhibition. In each run, the subjects look at a total of 224 visual stimuli that are sequentially presented in random order. Each stimulus is displayed for 500 ms, and any two neighbor stimuli are separated by a blank screen lasting 1900, 2100, or 2300 ms (uttered randomly). Each visual stimulus consists of lines enclosed within two boxes that are presented simultaneously side by side. The subjects are instructed to look at both boxes and to discriminate the direction of the lines. The subjects are instructed to press a button using their right index finger only when they see that both boxes show diagonal lines in the same direction in both boxes (Go trials). The subjects are instructed not to press any button when they see that both boxes show horizontal lines (easy-NoGo trials), or when they see that one box contains diagonal lines that are in the opposite direction of the diagonal lines in the other box (hard-NoGo trials). For Go trials, a correct response is defined as a key-press completed within 600 ms. For NoGo trials, an incorrect response is defined as a key-press completed within 600 ms. There are 168 Go trials (75%), 28 easy-NoGo trials (12.5%), and 28 Hard-NoGo trials (12.5%) in each fMRI run (10 min 40 s per run). For detailed descriptor, please see reference [1].

**C.4.7 Pre- and Post-treatment Behavioral Performance:** Because fMRI sessions in this project are conducted only during pretreatment baseline, this project will also acquire out-of-scanner pre-treatment and post-treatment (week 12) behavioral data for the cognitive tasks. Pre-treatment performance will be considered as a possible confounding factor and will be controlled as a covariate in the statistical analysis (Section C.4.20). Post-treatment behavioral performance is a treatment outcome and will be included in the treatment prediction analysis (C.4.20). In addition, [name], who is an expert in the behavioral science of drug addiction, will be a Consultant on this project to advise on the behavioral data implementation and analysis.

**C.4.8 MRI Scanning Site and Devices:** MRI sessions are conducted at the Magnetic Resonance Imaging Center of the UTHSC-H, using a research-dedicated Philips Intera 3.0 T MRI scanner with an 8-channel receive head coil (Philips Medical Systems, Best, Netherlands).

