Urn randomization [153], a form of stratified randomization, will help ensure comparability of treatment groups on baseline severity and duration of cocaine abuse. Pretreatment task behavioral performance or demographic variables on which group differences are detected, and which are correlated with outcomes, meet the definition of confounders [192, 193]. In such cases, analyses will evaluate the robustness of findings after statistically controlling for the confounder. If conclusions remain unchanged after covarying for the confounder, the more parsimonious model will be reported along with a statement indicating its robustness to covariation for potential confounding. If inclusion of the covariate alters the conclusions of the analysis, both models will be reported. Treatment success is a function of two elements: (a) retention and (b) demonstrating cocaine-free status using the SRPHK1 criteria (see section C.3.4). The Treatment Effectiveness Score (TES) provides a metric for this composite outcome [194]. TES is the sum of all cocaine-negative tests (according to SRPHK1 rules). Higher TES indicates that participants both continue to participate in the study and are negative for cocaine. For each group, BMA (section C.4.19.4) is conducted across all OCMs in the model space. Group difference in the gating effect by the dorsal striatum is assessed using Bayesian confidence probability [195]. In addition, BMA is conducted across all OCMs in the model space for each subject in the medication group and in the placebo group. Evaluation of differential treatment response, measured by the TES, as a function of the averaged (across the OCM model space) gating effect, will use Poisson regression. Violations of assumptions of dispersion will result in the use of more appropriate approaches such as zero-inflated Poisson, negative binomial, or zero-inflated negative binomial models. Regression of treatment, averaged gating, and their interaction will permit evaluation of differential treatment response as function of gating. The critical element in doing so is the evaluation of the interaction term. Given that the current study is powered to detect group differences, it is likely underpowered to detect an interaction. Brookes, et al. [196] demonstrate that for studies with 80% power to detect a between-groups effect, power to detect an interaction effect of the same magnitude as the main effect is approximately 29%. One solution is to adopt a Bayesian subgroup analysis approach [197-201]. This approach utilizes the posterior distribution of the interaction parameter to estimate the

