Urn randomization, a form of stratified randomization, will help ensure comparability of treatment groups on baseline severity and duration of cocaine abuse. Pretreatment task behavioral performance or demographic variables on which group differences are detected, and which are correlated with outcomes, meet the definition of confounders. In such cases, analyses will evaluate the robustness of findings after statistically controlling for the confounder. If conclusions remain unchanged after covarying for the confounder, the more parsimonious model will be reported along with a statement indicating its robustness to covariation for potential confounding. If inclusion of the covariate alters the conclusions of the analysis, both models will be reported. Treatment success is a function of two elements: (a) retention and (b) demonstrating cocaine-free status using the SRPHK1 criteria. The Treatment Effectiveness Score (TES) provides a metric for this composite outcome. TES is the sum of all cocaine-negative tests (according to SRPHK1 rules). Higher TES indicates that participants both continue to participate in the study and are negative for cocaine. For each group, BMA is conducted across all DCMs in the model space. Group difference in the gating effect by the dorsal striatum is assessed using Bayesian confidence probability. In addition, BMA is conducted across all DCMs in the model space for each subject in the medication group and in the placebo group. Evaluation of differential treatment response, measured by the TES, as a function of the averaged (across the DCM model space) gating effect, will use Poisson regression. Violations of assumptions of dispersion will result in the use of more appropriate approaches such as zero-inflated Poisson, negative binomial, or zero-inflated negative binomial models. Regression of treatment, averaged gating, and their interaction will permit evaluation of differential treatment response as function of gating. The critical element in doing so is the evaluation of the interaction term. Given that the current study is powered to detect group differences, it is likely underpowered to detect an interaction. Brookes, et al. demonstrate that for studies with 80% power to detect a between-groups effect, power to detect an interaction effect of the same magnitude as the main effect is approximately 29%. One solution is to adopt a Bayesian subgroup analysis approach. This approach utilizes the posterior distribution of the interaction parameter to estimate the probability that it exceeds some number (e.g., for Poisson regression a Risk Ratio of 1.0). Specification of vague neutral priors will reflect uncertainty regarding parameter values, utilizing prior distributions for the lower order effects that are neutral and diffuse with specification  $\sim N(0, 1 \times 10^{-6})$  on the log scale (i.e., centered at the null hypothesis with a 95% Credible Interval of  $\pm 1960$ ) for all coefficients, and  $\sim U(0, 100)$  for any required dispersion terms. Examination of the interaction of treatment and the subgroup index forms the crux of the evaluation of the subgroup effect. For evaluating the interaction representing the differential subgroup effect, analysis will be conducted in two ways: (a) utilizing diffuse, indifferent priors ( $\sim N(0, 1 \times 10^{-6})$ ) on the log scale for the interaction coefficients, and (b) using informative skeptical priors for the coefficients will evaluate sensitivity of statistical conclusions to specification of priors. Informative, skeptical priors will be derived via the method first proposed by Dixon and Simon. Evaluation of resulting posterior distributions will permit conclusions regarding the probability that subgroup/interaction effects of varying magnitudes obtain. Examples of this use of the posterior distribution may be found in Green et al. (2009). Bayesian modeling will use SAS v9.2 (Proc Genmod and Proc Monte-Carlo Markov chain [MCMC]), and in WinBugs 1.4.3 (<http://www.mrc-bsu.cam.ac.uk/bugs>). Convergence of Bayesian analyses on the posterior distributions via MCMC will be assessed via graphical (Trace Plot, Autocorrelation Plot) and quantitative (Geweke Diagnostics, Gelman-Rubin Diagnostics, and Heidelberger-Welsh Diagnostics) evidence. Evaluation of posterior distributions will permit statements regarding the probability that effects of varying magnitudes exist, given the data.

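### The confounder rule asks whether the conclusion changes, not the estimate, so a flagged confounder can leave only the unadjusted difference and interval in the report

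*SAP*

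**What the plan says.** The SAP's Data analysis plan, repeated in Protocol C.4.20 under Specific Aim 2, works in three steps.

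- **Definition.** "Pretreatment task behavioral performance or demographic variables on which group differences are detected, and which are correlated with outcomes, meet the definition of confounders".
- **Check.** For such a variable, "analyses will evaluate the robustness of findings after statistically controlling for the confounder".
- **Reporting.** "If conclusions remain unchanged after covarying for the confounder, the more parsimonious model will be reported along with a statement indicating its robustness". The more parsimonious model is the one without the covariate. Otherwise: "If inclusion of the covariate alters the conclusions of the analysis, both models will be reported". Neither model is then named as the main result.

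Two other places bear on this. Protocol C.4.7 states: "Pre-treatment performance will be considered as a possible confounding factor and will be controlled as a covariate in the statistical analysis", and refers the reader to C.4.20. For DLPFC–striatal connectivity (Aim 1), the Protocol and SAP also plan an analysis of covariance but name no covariates.

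**The concern.** An unchanged conclusion is weak evidence that the estimate is unchanged. The larger the true difference, the more easily significance survives adjustment, so the check is least sensitive where the effect is strongest. When it passes, the plan requires a statement of robustness but no adjusted estimate or interval, and a reader cannot see how far the figure moved.

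The rule also leaves open what counts as a conclusion. The Bayesian comparisons carry no posterior-probability threshold, so whether the rule is triggered would be judged after the results are known.

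At stake is the size of the cocaine-dependent v control differences. These groups are not randomised, and the Protocol presents effective connectivity as a possible biomarker, for which size matters as well as sign.

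**Working it through.** **1. The plan's own figures.** The documents give no figure for this rule. The two design figures borrowed below do reproduce: 24 / (1 − 0.20) = 30 recruited per group (C.4.1), and with 24 per group and an effect of 1.89 SD, two-sided alpha 0.05, power exceeds 0.999 (C.4.21 states 99.9%).

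**2. Where the rule can reach.**

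| Comparison | Randomised? | Link to the rule |
|---|---|---|
| Medication v placebo | Yes | Rule follows the urn-randomisation sentence under Aim 2 |
| Group difference in gating | No, if cocaine-dependent v control (C.4.19.4 runs the model averaging by those groups) | Same paragraph as the rule |
| Aim 3 | Both kinds | Analysis said to be essentially that of Aims 1 and 2 |
| Aim 1 | No | Separate text in the Protocol; the SAP has no Aim headings to confine the rule |

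**3. What being flagged implies.** The documents give no level for detecting a difference or correlation; 0.05 two-sided is assumed. With 24 v 24, t(0.975; 46) = 2.013. A group difference is detected only if the observed imbalance is at least 2.013 × √(2/24) = 0.58 SD. A correlation is detected only if |r| is at least 2.013 / √(46 + 2.013²) = 0.285. The gap between the two estimates equals slope × observed imbalance. At the detection limit, slopes of 0.3–0.5 give 0.3 × 0.58 = 0.17 to 0.5 × 0.58 = 0.29 SD.

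**4. Expected excess over all trials.** Assume a true imbalance of 0.6–0.8 SD and a covariate–outcome correlation within groups of 0.3–0.4. The unadjusted bias runs from 0.3 × 0.6 = 0.18 to 0.4 × 0.8 = 0.32 SD.

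- True difference 0.8 SD (assumed): 0.18/0.8 to 0.32/0.8, about 22–40%.
- True difference 1.89 SD (pilot value, C.2.4 and C.4.21): 0.18/1.89 to 0.32/1.89, about 10–17%.

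**5. Excess when the rule reports the unadjusted model alone.** Simulated trials used the same inputs, with 24 v 24 or 48 v 24 (24 medication + 24 placebo pooled, an assumption). A covariate was flagged at p<0.05 for both the group difference and the correlation. The conclusion was unchanged if both models gave the same significance at 0.05. Results are for trials that were flagged and unchanged.

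| True difference | Conclusion unchanged, among flagged | Reported unadjusted difference | Excess |
|---|---|---|---|
| 0.8 SD | about 75–81% (24 v 24), 87–91% (48 v 24) | 0.8 × 1.33 = 1.06 to 0.8 × 1.56 = 1.25 | about 33–56% |
| 1.89 SD | about 100% | 1.89 × 1.12 = 2.12 to 1.89 × 1.19 = 2.25 | about 12–19% |

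Across both rows the unadjusted 95% interval covers the truth in about 69–88% of trials, the adjusted one in about 95–97%. The excess is above step 4 because selecting flagged, unchanged trials favours larger observed differences. The same selection lifts the adjusted mean slightly, to 0.84–0.85 at a true 0.8 SD with 48 v 24.

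**6. Randomised arms.** With no true imbalance, about 2–5% of covariates are flagged at 24 v 24, and the unadjusted estimate has no systematic bias over repeated trials.

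**7. C.4.7 beside C.4.20.** C.4.7 has pretreatment performance controlled as a covariate, without condition. C.4.20 controls it only if it is flagged, as a robustness check whose estimate may go unreported.

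**The case against.** Five points can be made for the plan.

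- **Scope.** In the Protocol the rule belongs to Aim 2 and follows a sentence about comparability of the treatment groups. A reader might infer that the randomised treatment effect will be published in confounded form. The documents do not support that, because imbalance between those arms is chance. This stands, and it confines the concern to the non-randomised contrasts. Nothing in the SAP, however, limits the rule to the randomised arms.
- **Disclosure.** A reader might infer that the adjustment is hidden. It is not: the adjusted model is always fitted for a flagged variable, its agreement is stated, and both models appear if the conclusion changes. What is missing is the adjusted estimate and interval when it does not.
- **Aim 1 has an ANCOVA.** This stands, so an adjusted Aim 1 result may exist. With no covariates named, its content is open.
- **Matching.** Controls are matched on age, handedness and education, with equal numbers of men and women planned per group. A demographic imbalance of 0.6–0.8 SD is therefore on the high side, and task performance is the likelier flagged variable.
- **Adjustment may not be right for performance.** Section A.6 links cocaine use to altered working memory at behavioural and neuronal levels. Performance may be a consequence of dependence, and adjusting could remove part of the effect. The simulation treats the covariate as a pure confounder, which favours adjustment by construction. This stands, and rules out making the adjusted model primary for every flagged variable.

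On C.4.7, a reader might infer a flat contradiction. Since it calls performance a possible confounder and points to C.4.20, an inconsistency to reconcile is the fairer description.

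**Conclusion.** The concern holds as a reporting gap. When a variable is flagged and the conclusion does not change, the plan requires only the unadjusted estimate and interval, and an unchanged conclusion does not show that they are right. The harm is confined to the cocaine-dependent v control contrasts, if the rule is applied to them: the group difference in gating, its Aim 3 repeat, and Aim 1.

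The sizes in the working rest on assumed imbalance, correlation and flagging level. Only the 1.89 SD effect and the 24 per group come from the plan, and the percentage excess depends strongly on which true effect is assumed. The inconsistency between C.4.7 and C.4.20 depends on none of these assumptions. This is an inexpensive improvement to the reported effect size and does not put the treatment comparison in doubt.

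**What to change.** 1. In the SAP and C.4.20, replace the two reporting sentences with: *If a confounder is identified, the adjusted and unadjusted estimates are both reported with intervals, whether or not the conclusion changes; for demographic confounders in the non-randomised comparisons the adjusted model is the main result.* What gets reported then no longer depends on an undefined conclusion.
2. Name age, sex and education as covariates in the Aim 1 ANCOVA and its Aim 3 repeat. Age and education are already matching factors, and sex has a recruitment quota (C.4.1).
3. For task performance, show both estimates and state that the adjusted one may remove part of the effect of dependence.
4. Reconcile C.4.7 with C.4.20 so that both say the same about pretreatment performance.

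The cost is one to three degrees of freedom and one extra reported row per analysis. No new data are needed.

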Anatomically, OLPFC projects to the caudate, whereas limbic and paralimbic regions project to the ventral striatum [139, 140]. However, snOCM effective connectivity can be validly determined by indirect anatomical connectivity [141]. Thus, the connection from OLPFC to ventral striatum can be indirect via corticocortical intermediate connections [142, 143]. (b) The activity in the dorsal striatum was hypothesized to gate (positive modulation effect) the connectivity between the L IFC and the L PPC, based on O'Reilly and Frank [22]. Bayesian inference on model structure showed that the model in which the OLPFC causally affects the dorsal and ventral striatum had higher Bayesian exceedance probability ( $<1>=0.98$ ) than the model in which the ventral and dorsal striatum causally affects the OLPFC. The strength of the endogenous connection from DLPFC to ventral striatum was lower in the COs (-0.025 Hz) compared to controls (0.019 Hz) (Bayesian confidence probability  $> 0.999$ ; Cohen's  $d = 1.89$ ), but there was no significant difference between groups for dorsal striatum. These results are consistent with the corticostriatal circuits in addiction proposed in [85], in which increasingly repetitive or compulsive cocaine use is associated with progressively greater involvement of dorsal striatum but stable involvement of ventral striatum [144, 145]. Thus it is possible that in COs there is relatively less heterogeneity as a group in ventral striatum and relatively more heterogeneity in dorsal striatum. Heterogeneity in dorsal striatum is consistent with the above figure. This may explain why a significant average group difference was found in the connection from OLPFC to ventral striatum but not in the connection from OLPFC to dorsal striatum. Based on evidence [146-150] showing that glutamate has an excitatory effect on OA in striatum, it can be speculated that the lower (negative) strength of the connection from OLPFC to striatum in COs reflects

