**C.4.19.4 Inference on DCM parameters:** The inference on OCM parameters is conducted using Bayesian model averaging (BMA) [191]. BMA is a Bayesian approach that averages each OCM parameter across subjects and across models such that the contribution of each model (of each subject) for that parameter is weighted by each model's posterior probability for that subject. Thus, BMA avoids the rigid assumption of an identical single OCM for all subjects that is required in classical "Frequentist" analysis of OCM parameters [191]. The same model space, comprised of the optimal OCM for the COs group plus the optimal OCM for the control group, is used in the BMA analysis of each group to determine the posterior distribution of each OCM parameter for each subject within the group [138].

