C.4.21 Power Analysis: The power analysis was conducted using StudySize 2.0 software

(<http://www.studysize.com/>). The power analysis for the correlation analysis between the DCM striatal gating effect and the subsequent treatment outcome (Specific Aim 2) is based on the preliminary data (Section C.2.4). We have shown an effect size of 0.69 in our correlation analysis, but this is probably inflated due to the small sample size. Therefore we have conservatively used a more modest effect size of 0.60 when calculating the power. For an effect size  $d = 0.60$  and 2-tailed alpha = 0.05, a sample size of 24 subjects would achieve a power of 86% for the correlation analysis. For Specific Aim 1, our pilot data (Section C.2.4) showed an effect size of 1.89 for the between-group comparison of the strength of the endogenous connection from DLPFC to ventral striatum. Based on this effect size, we have calculated that 24 subjects per group would achieve a power of 99.9% at a 2-tail alpha = 0.05. Previous studies by our group [35, 37] (section C.2) found significant fMRI activation in predicted regions with 19 CDs and 14 controls. Thus we expect significant fMRI activation in the current project using the same fMRI task and scanning parameters with 24 subjects per group.

C.4.22 Limitations: OCM is based on several assumptions, especially in its original form [75]. However, we will use the OCM extensions, nonlinear [76] and stochastic [77] OCM, to reduce the dependence on these assumptions. OCM is a relatively new approach to study effective connectivity. However, OCM is being established as a primary effective connectivity technique in the neuroimaging literature, as evidenced by rapidly increased citation rates [78], overall publication number [203], and publication number in other patient populations [79], and high reliability has been shown in healthy subjects [80]. This project will only study COs who are treatment-seeking individuals, which may affect generalization of the findings to all COs. We believe that this is an acceptable trade-off because the major objective of this study is to develop a novel biomarker to predict treatment response in treatment-seeking COs.

1. Be between 18 and 50 years of age;
2. Right handed;
3. Have no past history of Psychiatric or non-Psychiatric medical disorders which could affect the central nervous system as assessed by SCID and physical examination.

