## Data analysis plan

Initial analyses will evaluate group differences on demographic and baseline variables, will use contingency tables with chi-square testing, ANOVA's, and examination of correlations between baseline variables and snDCM results. The Friston et al. network discovery technique, Bayesian model selection (BMS), and Bayesian family level inference (BFLI) will be used to select the optimal model based on the exceedance probability of the DCM (or family of DCMs) in which DLPFC causally affects ventral striatum vs. exceedance probability of the DCM (or a family of DCMs) in which the ventral striatum causally affects the DLPFC. The parameter estimates for the endogenous DLPFC-striatal connectivity will be compared between groups using Bayesian model averaging (BMA) and also compared using analysis of covariance.

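### As described, the group difference in dorsal-striatal gating rests on a Bayesian confidence probability alone, with no stated between-subject variance term, threshold, named groups or subject-level test

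*SAP*

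**What the plan says.** For Aim 2, the SAP (Data analysis plan) and Protocol C.4.20 begin with a model average at group level: "For each group, BMA is conducted across all DCMs in the model space". The next sentence gives the comparison: "Group difference in the gating effect by the dorsal striatum is assessed using Bayesian confidence probability". No second method, probability threshold or interval is named, and the text does not say which groups are compared.

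A separate step follows: "In addition, BMA is conducted across all DCMs in the model space for each subject in the medication group and in the placebo group". Those subject-level values feed the regression of the Treatment Effectiveness Score (TES) on treatment, gating and their interaction.

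Protocol C.4.19.4 explains the averaging: "BMA is a Bayesian approach that averages each OCM parameter across subjects and across models" (the text extraction shows DCM as OCM). Each model is weighted by its posterior probability for the subject. The same section ends by saying that the average is run in each group "to determine the posterior distribution of each OCM parameter for each subject within the group".

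For the Aim 1 connection from DLPFC to striatum, the SAP says that the estimates "will be compared between groups using Bayesian model averaging (BMA) and also compared using analysis of covariance". Aim 3 is to be analysed in essentially the same way as Aims 1 and 2 (Protocol C.4.20).

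**The concern.** A claim that two populations differ has to allow for how much people differ within each population. A parameter averaged over the scanned subjects, with a spread that reflects only estimation error and model uncertainty, describes those subjects. It says less about cocaine-dependent patients and controls in general, and a probability computed from it would be too close to 0 or 1.

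The plan accepts this principle elsewhere. Regional activation is analysed with a second-level random-effects model (Protocol C.4.17), and the Aim 1 connection gets an ANCOVA, which needs one value per subject. Gating has neither safeguard. Protocol C.2.4 also raises the possibility of greater heterogeneity among patients in the dorsal striatum, which is the gating node, but gives no figure.

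At stake are the stated certainty of the gating difference in Aim 2 and its repeat in Aim 3. In Aim 1, two methods are named with no statement of which one decides if they disagree.

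**Working it through.** **1. The plan's own group-comparison figure.** None is given for gating. For the Aim 1 connection, Protocol C.4.21 states that "24 subjects per group would achieve a power of 99.9% at a 2-tail alpha = 0.05", with d = 1.89.

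- Noncentrality: 1.89 × √(24/2) = 6.55.
- Normal approximation: Φ(6.55 − 1.96) = 0.999998. The noncentral t on 46 df gives 0.999996.

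The stated 99.9% is therefore reached. It belongs to a conventional two-sided test of connectivity, not to gating or to a Bayesian confidence probability.

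**2. What is stated for each comparison.**

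| | Aim 1 connection | Gating (Aim 2, repeated in Aim 3) |
|---|---|---|
| Group-level BMA | yes | yes |
| Second method | ANCOVA | none |
| Groups named | patients v controls | not named |
| Probability threshold | none | none |
| Between-subject variance term | not described for BMA | not described |

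**3. Size, if the pooled posterior omits between-subject variance.** Let each subject's estimate have within-subject posterior variance w, and let true values vary between subjects with variance b. Put R = b/w and take n subjects per group.

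- Variance the pooled posterior would use for the difference: 2w/n.
- Actual sampling variance of the difference: 2(w + b)/n.
- The ratio of the two is 1 + R, and n cancels.

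With no true difference, a rule of probability > c in either direction is met with probability 2 × [1 − Φ(z_c/√(1 + R))].

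R is not in the documents and the plan sets no c. Both are assumptions, so a range is shown. For c = 0.999, z_c = 3.09; for c = 0.95, z_c = 1.645.

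| Assumed R | c = 0.999 (nominal 0.2%) | c = 0.95 (nominal 10%) |
|---|---|---|
| 0.25 | 0.6% | 14.1% |
| 1 | 2.9% | 24.5% |
| 4 | 16.7% | 46.2% |
| 9 | 32.8% | 60.3% |

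Worked case: R = 4 gives 3.09/√5 = 1.382, and 2 × [1 − Φ(1.382)] = 16.7%.

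**4. Check by simulation** (200,000 replicates, 24 v 24, c = 0.999). The pooled rule was met in 2.8% of replicates at R = 1 and 16.7% at R = 4. A t test on subject-level estimates gave 0.19% and 0.20%, which is the nominal rate.

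**5. Does the pilot help?** Protocol C.2.4 reports for 6 v 6 subjects that "The strength of the endogenous connection from DLPFC to ventral striatum was lower in the COs", with a confidence probability > 0.999 and d = 1.89.

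- t = 1.89/√(2/6) = 3.27.
- On 10 df, the flat-prior probability is 0.9958.
- With the SD treated as known, Φ(3.27) = 0.9995.

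The second calculation includes the between-subject SD and still exceeds 0.999. The reported figure therefore does not separate the two explanations, and it concerns the connection to the ventral striatum, not gating.

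**The case against.** The strongest reply is that the documents never say between-subject variance is left out. The confidence probability is defined only by a citation, no formula is given, and C.4.19.4 also speaks of a posterior for each subject. A contrast built from those posteriors could carry the spread between people. This stands as far as it goes: the omission is an inference. Against it, the SAP introduces the subject-level averaging as an addition to the group-level one, and the gating comparison is attached to the group-level step. The pooled reading is therefore the natural one, and the plan would have to say so if something else were meant.

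Three stronger conclusions are tempting and should not be drawn.

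- **That the pilot demonstrates overstated certainty.** It does not, because 0.9995 can be reached with the between-subject SD included.
- **That Aim 2 as a whole is compromised.** Its critical element is the treatment-by-gating interaction in the TES regression. That uses subject-level gating and is untouched. The group difference is a supporting comparison with no power claim.
- **That the Aim 1 wording invites picking the more favourable answer.** The SAP says both methods will be used, and the power statement points to a conventional test. What is missing is only a statement of which result decides.

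It is also fair to say that the error rates depend on a ratio and a threshold that appear nowhere in the plan. At R = 0.25 the inflation is modest in absolute terms (0.6% against 0.2%).

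**Conclusion.** The point holds as a gap in the analysis specification. For gating, in Aim 2 and its Aim 3 repeat, the only stated group comparison is a probability that follows an average over subjects, with no between-subject variance term, threshold, named groups or subject-level test. If that probability reflects only within-subject and model uncertainty, a > 0.999 rule has a false-claim rate of about 0.6% to 32.8% for R from 0.25 to 9, against a nominal 0.2%. A larger sample would not reduce it. These rates are conditional on that reading, on the assumed R and on a threshold the plan does not set.

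This should be corrected before analysis, but it is not among the most serious faults a plan can have: the main Aim 2 analysis is unaffected, and Aim 1 already has a subject-level method.

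**What to change.** In Protocol C.4.20 and the SAP:

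- Name the groups in the gating comparison.
- Compare one BMA posterior mean of gating per subject, controls included where they form one of the groups. Use the ANCOVA already planned for Aim 1, or a hierarchical model with a between-subject variance term.
- Report the estimated difference with a 95% interval.
- State that this subject-level analysis also decides the group comparisons in Aims 1 and 3.
- Keep the pooled Bayesian confidence probability as a descriptive result, and state how it is computed.

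No new data are needed. The SAP lists subject-level averaging only for the medication and placebo groups, so it must be extended explicitly to controls; C.4.19.4 already describes subject-level posteriors within each group. The price is that extra processing and, probably, less favourable stated certainty.
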